5.5. Analysis Populations

Analysis populations except for biomarker are defined as follows:

CC-10004 (Apremilast)

Statistical Analysis Plan. Protocol CC-10004-PPP-001

- Intent-to-Treat Population

The intent-to-treat (ITT) population will be defined as all randomized subjects who received at least one dose of IP. Subjects will be included in the treatment group to which they are randomized.

- Safety Population

The safety population will include all randomized subjects who received at least one dose of IP. The analysis of safety data in this study will be based on the safety population and subjects will be included in the treatment to which they actually received. Safety analyses for the apremilast-exposure period will be based on the apremilast subjects as treated population, which will include all subjects who actually receive the apremilast 30 mg BID at the randomization visit or switched (at the Week 16 visit) to the apremilast 30 BID. Subjects will be included in the treatment sequence they actually received.

- Per-Protocol Population

The per protocol (PP) population will include all subjects in the ITT population who have no important protocol deviations that may substantially affect the efficacy results during the 16 weeks placebo-controlled treatment phase. The final determination of protocol deviation criteria to define the PP population will be made prior to the unblinding of the database and will be documented separately.

CC-10004 (Apremilast)

Statistical Analysis Plan. Protocol CC-10004-PPP-001

6. SUBJECT DISPOSITION

Subject disposition will be provided. The number of subjects screened, the number and percentage of subjects randomized and not randomized among all subjects screened will be summarized. The failed inclusion/exclusion criteria of subjects who were screened and not randomized will be included in the summary.

The number and percentage of subjects included in the ITT, PP, and safety analysis population and apremilast subjects as treated among all subjects randomized will be summarized.

The number of subjects who entered, and the number and percentage of subjects who completed, and discontinued of each phase will be summarized according to reasons of discontinuation.

Reasons for discontinuation will be summarized with the following categories in the eCRF:

- Adverse Event
- Lack of Efficacy
- Lost to Follow-up
- Pregnancy
- Death
- Protocol Deviation
- Study Terminated by Sponsor
- Withdrawal by Subject

A listing of subject eligibility/analysis population and a listing of subjects who discontinue the study early and reasons for discontinuation will be provided.

The number and percentage of subjects by site for ITT population will be tabulated.

CC-10004 (Apremilast)

Statistical Analysis Plan. Protocol CC-10004-PPP-001

7. PROTOCOL DEVIATION AND IMPORTANT PROTOCOL DEVIATION

The protocol deviations (PD) and important protocol deviations (IPD) will be identified and assessed by clinical research physician or designee. A list of PD and IPD for all subjects for Week 16 analysis will be defined prior to the Week 16 database restriction and unblinding (i.e., prior to the unblinding of double-blind placebo-controlled phase data). The list of PD and IPD for all subjects for final analysis will be finalized prior to the final DBL. This list of PD and IPD for Week 16 analysis will also identify which subjects are to be excluded from the PP population.

Summary tables showing the number and percentage of subjects with at least one PD and IPD and by each category of PD and IPD will be provided for the ITT population and subjects who entered active treatment phase. A by-subject listing of subjects with PD/IPD will be provided.

CC-10004 (Apremilast)

Statistical Analysis Plan. Protocol CC-10004-PPP-001

8. DEMOGRAPHICS AND BASELINE CHARACTERISTICS

The demographics and baseline characteristics will be summarized for the ITT population. Individual subject listings will be provided to support the summary tables.

8.1. Demographics

Summary statistics will be provided for the following continuous variables:

- Age (years)
- Weight (kg)
- Height (cm)
- Baseline Body Mass Index (BMI; kg/m²)

BMI will be programmatically calculated as BMI (kg/m²) = Weight (kg)/ Height (m²) based on the last weight measurement taken prior to the first dose of IP and the height measurement taken at screening.

Number and percentage will be provided for the following categorical variables:

- Age category (< 40, \geq 40 to < 65, \geq 65 to < 75, \geq 75)
- Sex (Male, Female)
- Ethnicity (Hispanic or Latino, Not Hispanic or Latino, Not Reported, Unknown)
- Race (American Indian or Alaska Native, Asian, Black or African American, Native Hawaiian or Other Pacific Islander, White, Not Collected or Unknown)
- Weight category (< 50, \geq 50 to < 60, \geq 60 to < 70, \geq 70 to < 85, \geq 85)
- BMI category (< 18.5, \geq 18.5 to < 25, \geq 25 to < 30, \geq 30)
- Tobacco Use (Current User, Past User, Non-User)
- Alcohol Use (Current User, Past User, Non-User)

8.2. Baseline Characteristics

Baseline clinical characteristics indicated below will be summarized descriptively:

- Duration of Palmoplantar Pustulosis (PPP) (time [in years] from first diagnosis to the informed consent date)
- Duration of PPP category (< 2, \geq 2 to < 6, \geq 6 to < 10, \geq 10 years)
- PPPASI score range based on IRT and clinical data (\leq 20, \geq 21 to \leq 30, \geq 31)
- Presence of focal infection based on IRT and clinical data (Yes/Presence, No/Absence)
- History of focal infection including periapical pathosis, periodontitis, tonsillitis, and sinusitis (Yes, No)
- Presence of pustulotic arthro-osteitis (PAO) (Presence, Absence, Unknown)

CC-10004 (Apremilast)

Statistical Analysis Plan. Protocol CC-10004-PPP-001

- Regular dental examination status (Presence, Absence)

8.3. Medical History

A summary of medical history will be presented by MedDRA version 21.1 or higher system organ class (SOC) and preferred term (PT). A similar summary will be generated for the currently active abnormalities only, by SOC and PT.

8.4. Prior and Concomitant Medications/Procedures

Prior medications/procedures will be summarized for the ITT population. Concomitant medications/procedures will be summarized for the safety population, apremilast subjects as treated, and subjects who entered the observational follow-up phase.

8.4.1. Prior and Concomitant Medications

Prior medications are defined as medications that were started before the start of the study treatment and either ended before the start of the study treatment or continued after study treatment. Concomitant medications are defined as medications that were either initiated before the first dose of IP and continued during the study treatment, or initiated on/after the date of the first dose of IP and on/before the date of treatment discontinuation. Medications initiated prior to the start of study treatment and were continued after the start of study treatment will be counted as both prior and concomitant medications.

The Anatomical Therapeutic Chemical (ATC) coding scheme of the World Health Organization Drug Dictionary (WHO DD version MAR 2019 or higher) will be used to group prior and concomitant medications into relevant categories.

A frequency tabulation of the number of subjects with the different types of prior and concomitant medications will be presented. Similar summaries will be provided for the prior and concomitant medications for palmoplantar pustulosis. A subject data listing of prior and concomitant medications will be provided.

8.4.2. Prior and Concomitant Procedures

Prior procedures are defined as those started before the first dose of IP (whether or not ended before the first dose of IP). Concomitant procedures are defined similarly as concomitant medications. The MedDRA will be used for coding. Frequency summaries of prior and concomitant procedures will be provided. A subject data listing of prior and concomitant procedures will be provided.

CC-10004 (Apremilast)

Statistical Analysis Plan. Protocol CC-10004-PPP-001

9. STUDY TREATMENTS AND EXTENT OF EXPOSURE

Study treatment and extent of exposure summaries will be provided on the safety population and apremilast subjects as treated. Descriptive statistics will be provided for treatment duration and compliance. A subject data listing of drug administration and accountability records will be provided.

9.1. Treatment Duration

Treatment duration will be descriptively summarized. Treatment duration (in weeks) is calculated as (the date of the last dose of IP – the date of the first dose of IP + 1) / 7. Imputation rule for partially or completely missing last dose date is specified in [Section 17.2.4](#). Summary statistics for treatment duration (in weeks), as well as a frequency summary of treatment duration categories (placebo-controlled phase: < 4, ≥ 4 to < 8, ≥ 8 to < 12, ≥ 12 to < 16, ≥ 16, active treatment phase: ≥ 16 to < 20, ≥ 20 to < 24, ≥ 24 to < 28, ≥ 28 to < 32, ≥ 32 weeks) will be provided.

Treatment duration for apremilast-exposure period is calculated from the date of the first apremilast administered, which is the date of the first administration of apremilast on/after the randomization at Week 0/Visit 2 or switched to apremilast at Week 16/Visit 10, to the last apremilast administered date for subjects who discontinue in the first 32 weeks or who complete the study at Week 32/Visit 14. Imputation rule for partially or completely missing last dose date is specified in [Section 17.2.4](#).

9.2. Treatment Compliance

For treatment compliance, descriptive statistics will be provided. The treatment compliance (%) for each subject will be computed as 100 times the total number of tablets taken (the total number of tablets dispensed minus the total number of tablets returned minus the number of tablets lost) over the period divided by the intended total number of tablets that should have been taken over the same period.

It is assumed that from the first through the last IP administered date, a subject takes the first 5 rows of tablets (6 tablets per row/day) on each complete blister card before taking the remaining rows (2 tablets per row/day), and completes the first 28 rows, skips rows 29-33 (5-day extra supply) and starts a new blister card, in case the subject visit at the planned date. It is also assumed that a subject takes the full day's tablets from a new blister card on a study drug dispense date.

The intended total number of tablets is calculated as

$$\text{The intended total number of tablets} = \begin{cases} 6 \times n & (\text{when } n < 6) \\ 30 + 2 \times (n - 5) & (\text{when } n \geq 6) \end{cases}$$

where n denotes the number of days between the returned date and dispensed date (ie, the date of return minus the date of dispense).

Summary statistics for compliance rate (%) will be provided. A frequency summary of compliance rate will also be presented with the following categories: < 75%, ≥ 75% to ≤ 100%, > 100% to ≤ 120% and > 120%.

CC-10004 (Apremilast)

Statistical Analysis Plan. Protocol CC-10004-PPP-001

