## 7. DESCRIPTION OF STUDY TREATMENTS

### 7.1. Description of Investigational Product(s)

The chemical name of apremilast (CC-10004) is *N*-{2-[(1*S*)-1-(3-Ethoxy-4-methoxyphenyl)-2-(methylsulfonyl)ethyl]-1,3-dioxo-2,3-dihydro-1*H*-isoindol-4-yl} acetamide.

Apremilast will be supplied by the Sponsor and labeled appropriately as IP for this study.

All IP will be provided in blister cards throughout the entire study. Apremilast will be provided as 10, 20, or 30 mg tablets. Placebo will be provided as identically appearing 10, 20, or 30 mg tablets. Apremilast, the IP, will be taken orally twice daily, approximately 12 hours apart, without restriction of food or drink. To mitigate potential GI side effects, dose titration will be implemented in the first week of this study (see [Table 6](#)).

During Week 0 (Days 1-7), subjects will be dispensed dose titration blister cards with 10, 20, and 30 mg apremilast tablets or identically appearing placebo tablets. The blister cards will contain all IP required for 4 weeks of treatment, with the first 7 days containing the titration supplies or matching placebo (see [Table 6](#) Treatment Schema for Dose Titration at Visit 2 [Week 0] which details the titration supplies from Day 1 to Day 7).

At Visit 2 (Week 0), subjects who meet eligibility criteria will be randomized using a permuted block randomization in parallel 1:1 to receive either apremilast 30 mg BID or placebo, using a centralized IRT. IP will be dispensed as indicated below.

- Weeks 0 to 16: double-blind, placebo-controlled phase: apremilast 30 mg BID or placebo BID.
  - Week 0 to 1: subjects will be dose titrated as described above and detailed in [Table 6](#).
- Weeks 16 to 32: active treatment phase: apremilast 30 mg BID
  - Week 16 to 17: Subjects will be dose titrated as described below and detailed in [Table 7](#)

Starting at Week 16, all subjects will receive apremilast. Subjects originally randomized to placebo at Week 0 will be switched to apremilast 30 mg BID at Week 16 and dose titration blister cards will be used. Dummy titration blister cards (dosing at 30 mg BID directly) will be used for subjects originally randomized to apremilast 30 mg BID. At all other visits during the active treatment phase, all subjects will receive apremilast 30 mg tablets which are to be taken twice daily.

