During Weeks 16 to 32, the IP will remain blinded, to prevent study personnel and subjects from knowing the IP assignment in the double blind, placebo-controlled Phase (Week 0 to 16) and to maintain the blind regarding the initial treatment assignment, all subjects will receive dose titration cards at Visit 10 (Week 16). Although only subjects initially randomized to placebo will be dose titrated during their first week of the active treatment phase, all subjects entering the active treatment phase will receive identically-appearing titration/treatment cards as shown in [Table 7](#).

Please refer to local apremilast prescribing information for more details on available formulations, preparation, storage conditions, the approved indications, known precautions, warnings, and adverse reactions of apremilast (see current version of Prescribing Information). The apremilast dosing schedule and dose adjustments to be followed for this study are described in [Section 7.3](#).

Additional information may be included on the label as needed or applicable. Label(s) for IP will contain information as required per local health authority.

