## 7.3. Treatment Administration and Schedule

IP will be taken orally twice daily, approximately 12 hours apart, without restriction of food or drink. To mitigate potential GI side effects, dose titration will be implemented in this study. During Week 0 (Days 1 to 7) and Week 16 (when placebo subjects are switched to receive apremilast 30 mg BID), subjects will be dispensed blister cards with 10, 20, and 30 mg apremilast tablets or identically appearing placebo for the dose titration.

At all other visits where IP is dispensed, apremilast will be provided in blister cards as 10, 20, and 30 mg tablets or identically appearing placebo tablets. The treatment schema for dose titration at baseline (Week 0) and Week 16 is shown in [Table 6](#) and [Table 7](#), respectively.

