## **7.8. Investigational Product Compliance**

Study personnel will review the instructions printed on the package with the study subjects prior to dispensing the IP. IP will be dispensed as indicated in ([Table 5](#)). The subjects will be instructed to return the IP blister cards, including any unused IP, to the study site at each visit for pill counts and reconciliation. Subjects will be asked whether they have taken their IP as instructed at each study visit. Any problems with IP compliance will be reviewed with the subject. If a subject misses 4 or more consecutive days of dosing, Amgen should be contacted to

decide whether dosing should resume or whether the subject should be terminated from the Treatment phase of the study and enter into the Observational follow-up phase.

Gross compliance problems (eg, missing 4 or more consecutive days of dosing or taking less than 75% of the doses between study visits) should be discussed with Amgen. Compliance is defined as taking between 75% and 120% of dispensed IP of the expected doses during a subject's participation while in the treatment phases (double blind, placebo-controlled phase and active treatment phase) of the study. This definition of compliance is only for the purpose of study analysis, not study conduct.

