5.2.1. Analysis Periods

Per protocol specification, data summary and analysis will be provided for the following periods, if appropriate.

- Placebo-controlled Phase/Period

This period starts on the day of randomization (Week 0/Visit 2), and stops on below, whichever is later:

- (1) the day of Week 16/Visit 10 if the subject continued study treatment to the active treatment phase
- (2) the day of the discontinuation if the subject discontinued study treatment prior to or at Week 16/Visit 10
- (3) the last known study day if the subject is lost to follow-up prior to Week 16/Visit 10

CC-10004 (Apremilast)

Statistical Analysis Plan. Protocol CC-10004-PPP-001

The two treatment arms are apremilast 30 mg BID or Placebo.

- Active Treatment Phase/Period

This period starts on one day after the day of the first dose of apremilast at Week 16/Visit 10, and stops on either below.

- (1) the day of Week 32/Visit 14
- (2) the day of the discontinuation if the subject discontinued prior to or at Week 32/Visit 14
- (3) the last known study day if the subject lost to follow-up prior to Week 32/Visit 14 during the phase

The two treatment arms are 30 mg BID/30 mg BID, and Placebo/30 mg BID.

For safety analysis, the period starts on the day of the first dose of apremilast in the period.

- Observational Follow-up Phase/Period

Subjects who complete or discontinue the study treatment, will be followed up for 28 days after last dose of IP.

For adverse event analysis, data from the first 28 days after the last dose of IP will be included in the precedent treatment phase and data after the 28 days will be presented separately.

- Apremilast-exposure Period

This period starts on the date of either:

- (1) the first dose of IP following randomization (Week 0/Visit 2) for subject who are treated with apremilast from Week 0
- (2) the first dose of IP from the IP dispensed at Week16/Visit 10 for subjects who were originally treated with placebo and are switched to apremilast at Week 16

This period stops on either: (1) data restriction date; or (2) the end of the study.

During the apremilast-exposure period, data are presented by treatment sequence, i.e., Placebo/30 mg BID, 30 mg BID as Initiated, and a total column of 30 mg BID as Treated.

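### Does SAP 9.2 count too many intended tablets for blister cards dispensed after the titration card?

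*SAP*

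**What the plan says.** SAP 9.2 defines compliance as 100 times tablets taken (dispensed minus returned minus lost) divided by intended tablets over the same period. For the intended count it assumes that the subject "takes the first 5 rows of tablets (6 tablets per row/day) on each complete blister card", then takes two tablets per row, "completes the first 28 rows, skips rows 29-33 (5-day extra supply) and starts a new blister card". With n equal to the return date minus the dispense date, intended tablets are 6n for n below 6 and 30 + 2(n − 5) from n = 6 onwards. There is no exception by type of card.

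The protocol describes card contents in two places. Section 7.1 says of titration that "all subjects will receive dose titration cards at Visit 10 (Week 16)", and of the rest of that phase: "At all other visits during the active treatment phase, all subjects will receive apremilast 30 mg tablets which are to be taken twice daily". Section 7.3 says: "At all other visits where IP is dispensed, apremilast will be provided in blister cards as 10, 20, and 30 mg tablets", or matching placebo.

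Protocol 7.8 sets the limits: "Compliance is defined as taking between 75% and 120% of dispensed IP of the expected doses". It adds that the definition serves study analysis and not study conduct. SAP 9 states where the result goes: "Study treatment and extent of exposure summaries will be provided on the safety population and apremilast subjects as treated". In the apremilast-exposure period, "data are presented by treatment sequence, i.e., Placebo/30 mg BID, 30 mg BID as Initiated", with a total column.

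**The concern.** Read alone, the sentence in Protocol 7.1 contrasts the remaining active-phase visits with the titration visits and seems to leave two tablets a day on the Week 20, 24 and 28 cards. The SAP formula would then charge each of those cards with 20 tablets that it never held. A subject who took everything would appear about 20 points short, and the class below 75% would take in people who had missed few tablets. The two sequences in the apremilast-exposure table would also differ for a reason unrelated to behaviour, because the affected cards are a larger share of the shorter exposure.

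A second gap adds to this. The formula is written for one dispense-to-return interval, and SAP 9.2 does not say in words that intervals are added up over the period.

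**Working it through.** **Inputs.** Five rows of six tablets, then two per row, 28 rows used per card (SAP 9.2). Dispensing at Weeks 0, 4, 8, 12, 16, 20, 24 and 28 (Protocol Table 5), so four cards per phase. Titration cards at Weeks 0 and 16 (Protocol 7.1, Tables 6 and 7). Two tablets a day on other active-phase cards is one reading of Protocol 7.1, not a stated count.

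**The SAP's own figure.** At n = 28 the formula gives 30 + 2 × 23 = 76. The titration layout gives 5 × 6 + 23 × 2 = 76, so the formula is exact for that card. The branches join without a jump: n = 5 gives 30 and n = 6 gives 32.

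**If the Week 20, 24 and 28 cards hold two a day, summed by card.**
- Content per 28 days: 2 × 28 = 56, so the overcharge is 76 − 56 = 20 per card.
- Active phase, full adherence: (76 + 3 × 56)/(4 × 76) = 244/304 = 80.3%.
- Shortest permitted phase (Week 16 two days late, Week 32 four days early, 106 days): (2 × 106 + 20)/(2 × 106 + 80) = 232/292 = 79.5%. Longest (118 days): 256/316 = 81.0%.
- True adherence that would be shown as 75%: 0.75 × 304/244 = 228/244 = 93.4%.
- Apremilast exposure, full adherence: 80.3% for Placebo/30 mg BID, against (4 × 76 + 244)/(8 × 76) = 548/608 = 90.1% for 30 mg BID as Initiated.
- If the Week 4, 8 and 12 cards were also two a day, which Protocol 7.1 does not say, the second figure becomes 488/608 = 80.3% and the gap between sequences vanishes.

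**If every card has the six-tablet rows, summed by card.** 304/304 = 100%. There is no error.

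**The unstated summation.** Applied once to the 112-day phase, the formula gives 30 + 2 × 107 = 244. A full complier would then show 244/244 = 100% with two-a-day later cards, and 304/244 = 124.6% with six-tablet rows throughout. The 80.3% therefore needs both the two-a-day layout and summation by card.

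**Which layout do the documents support?** SAP 9.2 gives a row-by-row description, including a five-row reserve, and applies it to each complete card. Protocol 7.3, the administration section, addresses the other dispensing visits directly and lists all three strengths. Protocol 7.1 names the active tablet and its frequency but does not say that nothing else is on the card. The same section describes the Week 16 card for subjects already on apremilast as going straight to 30 mg twice daily, while Table 7 shows 10 mg and 20 mg placebo tablets beside the 30 mg tablets on it. In this protocol, then, 30 mg twice-daily language can describe the active dose on a card that has six-tablet rows.

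**The case for a change.** The best case for a change is that no passage closes the question. The phrase about all other visits in Protocol 7.1 does set those cards apart from the titration cards, and read that way it cannot be squared with SAP 9.2. With two possible layouts and two ways of applying the formula, a full complier could be shown at 80.3%, 100% or 124.6%, and the last lies outside the protocol's own 75% to 120% range. The remedy would be cheap.

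Part of this stands: the wording is loose, and the summation is left to inference. But the inference is easy. SAP 9.2 speaks of each complete card, defines n from that card's dispense and return dates, and has the subject start a new card after 28 rows, so summing over cards is the natural reading and 124.6% is not a realistic output. The layout does not stay hidden either, because the numerator starts from tablets dispensed. A 33-row card with six-tablet rows holds 5 × 6 + 28 × 2 = 86. A two-a-day card, if it also had 33 rows (an assumption, since the SAP describes no such card), would hold 66, fewer than the 76 it was meant to supply in 28 days. A programmer would meet that mismatch on the first card.

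**Conclusion.** No change to the plan follows. The arithmetic behind 80.3% is correct, but it rests on a card layout that the documents do not establish and that SAP 9.2 and Protocol 7.3 speak against. On the layout those two describe, summed by card, the formula is exact.

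Little would be at stake even on the unfavourable reading. Compliance is summarised descriptively. The primary analysis on the intent-to-treat population does not use it, and no passage ties the per-protocol population to it. A full complier who keeps to the visit windows would show at least 79.5% over the active phase and so stay out of the class below 75%. In the placebo-controlled phase both arms receive the same pattern of cards, so the randomised comparison of compliance would not be tilted. The gap of about 10 points between sequences (90.1% against 80.3%) arises only if exactly the three later active-phase cards are affected.

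What remains is an imprecise sentence about packaging in Protocol 7.1 and a summation step that an analyst would supply. The wording of Protocol 7.1, Protocol 7.3 and SAP 9.2 can be reconciled against the manufactured card in ordinary programming checks. This conclusion assumes that the later cards carry the six-tablet rows. If the card counts showed otherwise, the denominator for those cards would need to follow their actual content.

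### SAP 9.2 counts intended tablets up to the card's return date, so compliance is understated for a subject who permanently stops treatment and returns the final card more than one day later

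*SAP*

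**What the plan says.** SAP 9.2 computes each subject's compliance as 100 times tablets taken over tablets intended for that period. Tablets taken are "the total number of tablets dispensed minus the total number of tablets returned minus the number of tablets lost". The intended number is 6n when n is below 6 and 30 + 2(n − 5) otherwise, "where n denotes the number of days between the returned date and dispensed date". No separate rule is given for a subject who stops treatment for good.

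The same section describes how the cards are used: "It is assumed that from the first through the last IP administered date, a subject takes the first 5 rows of tablets" (six tablets a day) and then the two-tablet rows. On that description, card use ends with the last dose. SAP 9.1 likewise ends treatment duration at "the date of the last dose of IP", and SAP 17.2.4 imputes that date when it is partly or wholly missing.

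Results are tabulated with a lowest category of below 75%. Protocol 7.8 defines compliance as "taking between 75% and 120% of dispensed IP of the expected doses" and says the definition serves analysis only, not study conduct.

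Protocol 6.2.1 asks for the end-of-treatment evaluation promptly after the decision to stop, but sets no maximum gap. Protocol Table 5 schedules tablet counts at Weeks 4, 8, 12 and 16, every four weeks after that, and at early termination.

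**The concern.** The numerator stops at the last dose, because nothing is taken afterwards. The denominator carries on until the card comes back. After a permanent stop no tablets are due, yet each further day before return adds two intended tablets, or six while n is still below 6. This conflicts with the section's own assumption about when the card is in use, and with its instruction that both counts cover one period. It also makes the exposure table (SAP 9.1) and the compliance table (SAP 9.2) describe different periods for the same subject.

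What is at stake is the accuracy of the reported percentage and of the below-75% category, which coincides with the protocol's lower limit for compliance. A subject with perfect intake until stopping can be placed in that category.

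**Working it through.** **Inputs.** Intended tablets from SAP 9.2: I(n) = 6n for n < 6, and 30 + 2(n − 5) for n ≥ 6. Card layout from SAP 9.2: five rows of six tablets, then rows of two. Dispensing is on Day 1. The return days are assumptions, since the documents give no gaps.

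**1. The plan's formula against its card layout.** The SAP states no numeric compliance result, so the formula itself is checked. Over 28 rows the layout holds 5 × 6 + 23 × 2 = 76 tablets, and I(28) = 30 + 2 × 23 = 76. A row-by-row count agrees for every n from 0 to 33.

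**2. A continuing subject.** A card dispensed on Day 1 and exchanged on Day 29 has n = 28. Doses on Days 1 to 28 come from it, and the Day 29 dose comes from the new card. Compliance is 76/76 = 100%, so the rule is right here.

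**3. A permanent stop on the first card.** With every tablet taken through Day k and the card returned on Day r, tablets taken = I(k), n = r − 1, and compliance = 100 × I(k)/I(r − 1). The undosed days counted are r − 1 − k.

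| Last dose | Return | Undosed days counted | Taken | n | Intended | Compliance |
|---|---|---|---|---|---|---|
| Day 5 | Day 6 | 0 | 30 | 5 | 30 | 100% |
| Day 5 | Day 12 | 6 | 30 | 11 | 42 | 71.4% |
| Day 6 | Day 13 | 6 | 32 | 12 | 44 | 72.7% |
| Day 10 | Day 17 | 6 | 40 | 16 | 52 | 76.9% |
| Day 10 | Day 18 | 7 | 40 | 17 | 54 | 74.1% |
| Day 10 | Day 29 | 18 | 40 | 28 | 76 | 52.6% |

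The correct value is 100% in every row.

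**4. How long a gap takes the result below 75%.** On the first card, the smallest number of undosed days is 1 after one or two days of dosing, 2 after three days, 6 after five or seven, 7 after ten, 9 after fourteen and 11 after twenty-one.

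**5. Stops on later cards.** It is not clear whether every later card carries six-tablet rows: SAP 9.2 describes them for each card, while Protocol Tables 6 and 7 show titration only at Week 0 and Week 16. Both layouts are therefore shown as a range, for a stop ten days into the card:

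| Full cards before | Compliance, 7 undosed days | Undosed days needed for <75% |
|---|---|---|
| 1 | 87–89% | 17–20 |
| 2 | 92–93% | 26–33 |
| 3 | 94–95% | 35–45 |

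A stop within the first days of a second card with six-tablet rows crosses sooner. One day in, with 6 undosed days, gives (76 + 6)/(76 + 34) = 82/110 = 74.5%.

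**6. Last dose on the return day.** Here n is one day short. For Day 5, n = 4 and compliance is 30/24 = 125%, above the SAP's 120% boundary. For Day 14, it is 48/46 = 104.3%.

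**7. With n ended at the last dose.** For the final card, n = last dose date − dispense date + 1 = k, so compliance is I(k)/I(k) = 100% whatever the gap, including cases 3 and 6.

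**The case against.** First, the protocol wants a prompt end-of-treatment visit, and Table 5 has tablets counted at early termination, so long gaps should be uncommon. The 52.6% example, with return at the scheduled Day 29 visit, looks more like someone who quietly stopped dosing, which is real non-adherence. This stands as a limit on size. It does not remove the error, because no maximum gap is set and a week's delay after an early stop is enough.

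Second, the figure feeds only descriptive tables, and drug administration and accountability records are listed by subject. That stands. The primary analysis uses the intent-to-treat population with non-responder imputation and makes no use of compliance.

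Third, ending n at the last dose can hide missed dosing just before withdrawal. A subject who silently stops on Day 10 and returns the card on Day 29 would move from 52.6% to 100%, although Protocol 7.8 treats four or more consecutive missed days as a gross compliance problem. That stands, and the change has to allow for it.

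**Conclusion.** The rule is wrong as written for one group: subjects who permanently stop treatment and return the final card more than one day after the last dose. Their compliance is understated. Some can be reported below 75% despite taking every tablet until they stopped, mainly after a stop in about the first two weeks with a gap of about a week or more. The sizes rest on assumed gaps. Severity is minor.

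Three stronger readings are tempting, and the documents do not support them.

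- **That every such subject is reported as non-compliant.** A last dose on Day 10 with return on Day 17 gives 76.9%, and complete earlier cards dilute most later stops.
- **That the error makes adherence on apremilast look worse than on placebo.** Protocol 6.5.5 cites post-marketing gastrointestinal events, mostly in the first weeks, so more early stops on apremilast are plausible. But no discontinuation rates by arm are given, titration is meant to reduce these events, and lack of efficacy is also a listed reason to stop. Neither direction nor size can be established.
- **That it alters the per-protocol population.** SAP 5.5 leaves those criteria to a separate document fixed before unblinding, and nothing says that this percentage enters them.

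**What to change.** In SAP 9.2, define n by card. For the final card of a subject who permanently stops treatment, n = date of last dose − date of dispense + 1, using the SAP 17.2.4 imputation if the last dose date is missing. For all other cards, n = date of return − date of dispense, as now. Keep the return-date rule for the final card as well when the recorded reason for stopping is non-compliance with treatment, so that silent missed dosing still counts. Protocol 11.1 lists that reason but the categories in SAP 6 do not, so the text should say where it is read from.

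The cost is a sentence or two of SAP text and a small change to the derivation, using a date already derived for SAP 9.1. Some error remains:

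- A completely missing last dose date may be imputed from the discontinuation visit, which brings the gap back.
- A silent stop recorded under another reason would score too high.
- A final day with only the morning dose would score slightly low. For Day 5 this is 27/30 = 90.0%, against 27/24 = 112.5% now if the card is returned that day.
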